7.2 Sharing of genetic testing: NA

8.0 Study Population

8.1 Inclusion Criteria: Healthy children aged 1 month – 17 years.

8.2 Exclusion Criteria:

- Fever or hypothermia
- Chronic illness including cardiovascular or renal disease
- Severe injury or blood loss

MEDICAL PROTOCOL (HRP-590)

PROTOCOL TITLE: Capillary Refill Time Measurement Utilizing Mobile Application (Cap App) in Children

VERSION DATE: 10/27/2022

- Dehydration (including vomiting and/or diarrhea)
- Raynaud's phenomenon
- Children who do not have a parent or legal guardian present to obtain consent

8.3 Screening: Convenience sample of participants presenting at the D2D: The Driven to Discover Research Facility at the Minnesota State Fair August 25 - September 5, 2022 will be screened for inclusion and exclusion criteria. All those who are eligible will have the opportunity to enroll. We will utilize a script to assist in the screening process to ensure that all information is presented accurately and uniformly to all potential participants.

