15.3 Statistical Analysis: We will recruit pediatrics patients aged 1 month to 17 years who are presenting to the D2D: The Driven to Discover Research Facility at the Minnesota State Fair. Descriptive statistics will be used to summarize the data collected. For the primary outcome, we will calculate mean CRT along with 95% confidence intervals, both overall and by age group, sex, and skin tone. We will attempt to enroll a minimum of 48 patients per age group for a total of 240 patients. Initial results showed an average standard deviation of 0.663 seconds across all patients at normal hand temperature. When the sample size is 48, a two-sided 95% confidence interval for a mean will extend ± 0.188 seconds. For a total sample size of 240, a two-sided 95% confidence interval for a mean will extend ± 0.084 seconds. Human annotation of a video recording using a stopwatch will be used to measure the manual CRT measurement and we will perform computer annotation of the video recording as a gold standard. For human and computer annotations we will calculate inter-rater reliability by repeating annotations with a different observer on 10% of a random group of CRT measurements. Inter-rater reliability will be evaluated using intraclass correlation coefficients (ICCs) and Bland–Altman plots.

15.4 Data Integrity: The research assistant will obtain study eConsent and fill the data collection forms which will be embedded into the Cap App and will be password protected. The data forms, video recordings for human and computer annotation, and Cap App CRT measurement will then be uploaded to a secure web-based data storage platform, Box. The research assistant will erase the data on the smartphones every shift and will store them in a secure location at all times. The *consent forms, assent forms, and case report forms* will be electronic (UMN REDCap eConsent). No paper copies will be utilized.

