Indicate if data will be collected, downloaded, accessed, shared or stored using a server, desktop, laptop, external drive or mobile device (including a tablet computer such as an iPad or a smartform (iPhone or Android devices) that you have not already identified in the preceding questions

I will use a server not previously listed to collect/download research data

I will use a desktop or laptop not previously listed

I will use an external hard drive or USB drive ("flash" or "thumb" drives) not previously listed

I will use a mobile device such as a smartphone not previously listed: The demographics, vital signs, underlying diagnosis, and CRT data (including video for the manual CRT measurement) will be collected from a smartphone which is running the Cap App mobile phone application. The data collected will be de-identified and uploaded to a secure Box platform hosted by UMN.

16.8 Consultants. Vendors. Third Parties. : A DUA will be signed to share de-identified research data with The University of Washington and The University of Toronto, who are collaborators on the CapApp.

16.9 Links to identifiable data:

All data will be de-identified. Study staff will assign an identification code for each participant to identify each individual record but it will not be used to link back to each individual participant. That same identification code will be transferred into the Box database. Any internal data reports will use only these codes and will not use any identifiable information. Any external data reports, abstracts, publications, presentations, etc. will present de-identified, grouped, and/or aggregate data. Any reports to the University of Minnesota IRB (such as Adverse Event reporting and annual renewal reports) will be kept confidential; they will not include participant- identifiable information; only the participant's identification code will be used

MEDICAL PROTOCOL (HRP-590)

PROTOCOL TITLE: Capillary Refill Time Measurement Utilizing Mobile Application (Cap App) in Children
VERSION DATE: 10/27/2022

- 16.10 Sharing of Data with Research Team Members Only* IRB-approved members of the study team will have access to the data through the methods already indicated in this section.

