21.0 Consent Process

21.1 Consent Process (when consent will be obtained):

Participants will self-report with interest at the D2D: The Driven to Discover Research Facility at the Minnesota State Fair.

- The consent will take place in the research space provided at the D2D: The Driven to Discover Research Facility.
- There is no built-in waiting period available between informing the prospective participants and obtaining the consent. If the subject requests a waiting period to help make an informed decision, a reasonable time will be allotted to accommodate that request as deemed appropriate by the treating provider.
- We will provide a copy of the current ICF to the participant, in advance if possible.
- ICF will be read to the participant after which questions will be invited and responded to.
- The participant will be given time to discuss consent with others, including taking ICF home to consider.
- The researcher will determine if the potential participant understands the information presented through the consent process and

MEDICAL PROTOCOL (HRP-590)

PROTOCOL TITLE: Capillary Refill Time Measurement Utilizing Mobile Application (Cap App) in Children

VERSION DATE: 10/27/2022

comprehends study details. It is under the discretion of the researcher, and per D2D requirements, that if there is suspect of alcohol intoxication, consent will not proceed at that time.

- We will obtain consent from one parent/legally authorized representative and assent from the participant if old enough.
- This will be obtained by electronically in-person utilizing the D2D provided devices (i.e. iPads) with electronic signature capture.
- An electronic copy of the signed ICF/HIPAA forms will be emailed to the participant.
- We will ensure ongoing consent through voluntary participation in the study including performing the procedure. We will ensure voluntary participation at each stage of the study through verbal confirmation.

21.2 Waiver or Alteration of Consent Process (when consent will not be obtained): NA

21.3 Waiver of Written/Signed Documentation of Consent (when written/signed consent will not be obtained): A script will be used to screen potential participants for enrollment, prior to obtaining consent. This script will ensure that all information is presented accurately and uniformly to all potential participants. No PHI or study procedures will occur until formal consent process is conducted and signed consent/assent is provided.

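### The intervals for mean CRT treat all children as unrelated, but siblings may enrol and no family identifier is planned, so the intervals may be too narrow

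*Combined protocol and SAP*

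**What the plan says.** For the primary outcome, Section 15.3 says that "we will calculate mean CRT along with 95% confidence intervals, both overall and by age group, sex, and skin tone". The planning inputs are in the same section: "Initial results showed an average standard deviation of 0.663 seconds across all patients at normal hand temperature", and "We will attempt to enroll a minimum of 48 patients per age group for a total of 240 patients". Two half-widths follow: "When the sample size is 48, a two-sided 95% confidence interval for a mean will extend ± 0.188 seconds", and "For a total sample size of 240, a two-sided 95% confidence interval for a mean will extend ± 0.084 seconds". No term for family or any other cluster is mentioned.

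On who enrols, Sections 8.3 and 11.1 describe a convenience sample at the Minnesota State Fair, and Section 8.2 requires a parent or guardian to be there. Section 8.3 adds: "All those who are eligible will have the opportunity to enroll". Neither the eligibility criteria nor the table in Section 9.1 limits enrolment to one child per family.

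On the data, the fields listed in Sections 4.0 and 5.1 include a study ID, demographics, temperatures, vital signs and diagnosis, but no family or household number. Section 16.9 says of the study code that "it will not be used to link back to each individual participant". Section 17.1, however, keeps a separate log of names against identifiers and holds the consents in REDCap, and Section 19.1 gives the principal investigator and designated staff access to the linkages.

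**The concern.** Ages from 1 month to 17 years are eligible, the venue attracts families, and a parent must attend, so enrolment of siblings is foreseeable. Siblings can resemble each other in CRT. Section 2.1 reports that in the adult pilot the app read longer in the cold and tended to overestimate in darker skin. Siblings often share skin tone, and siblings measured in one visit share room conditions.

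If so, 240 children carry less information than 240 unrelated children, and an interval computed under independence covers the true mean less often than 95% of the time. This matters because Section 15.2 gives precision as the goal and reports no formal power calculation. The half-widths in Section 15.3 are therefore the only quantitative support for the sample size, and the intervals are the stated primary analysis. Section 6.0 also foresees de-identified data going to other researchers, who could not allow for families without a family key.

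**Working it through.** **Inputs from Section 15.3.** SD 0.663 s; n = 240 in total and 48 per age group; two-sided 95% level.

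**Reproducing the plan.** Half-width = 1.96 × SD / √n.
- n = 240: 1.96 × 0.663 / √240 = 0.0839, which rounds to the stated 0.084.
- n = 48: 1.96 × 0.663 / √48 = 0.1876, which rounds to the stated 0.188.

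The arithmetic is right, and the formula is the one for independent children.

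**Allowing for siblings.** The design effect is DEFF = 1 + (Σm²/Σm − 1) × ICC, where m is the number of enrolled children per family and ICC is the correlation between siblings. The half-width becomes 0.0839 × √DEFF, the effective sample size 240/DEFF, and the actual coverage of the uncorrected interval 2Φ(1.96/√DEFF) − 1.

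The documents give neither m nor ICC, so the following are assumptions:
- (a) 80% of families bring one child and 20% bring two: Σm²/Σm = 1.6/1.2 = 1.33.
- (b) 60/30/10% bring one/two/three: 2.7/1.5 = 1.80.
- (c) 30/50/20% bring one/two/three: 4.1/1.9 = 2.16.

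| Mix | ICC 0.1 | ICC 0.3 | ICC 0.5 |
|---|---|---|---|
| (a) DEFF; half-width | 1.03; ±0.085 | 1.10; ±0.088 | 1.17; ±0.091 |
| (b) DEFF; half-width | 1.08; ±0.087 | 1.24; ±0.093 | 1.40; ±0.099 |
| (c) DEFF; half-width | 1.12; ±0.089 | 1.35; ±0.097 | 1.58; ±0.105 |

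These cells correspond to effective sample sizes from 232 down to 152, and to coverage from about 94.6% down to 88%. An extreme case with Σm²/Σm = 2.0 and ICC 0.6 gives DEFF = 1.60, effective n = 150 and 0.0839 × √1.60 = ±0.106 s. With no siblings, or ICC = 0, the figure stays at ±0.084 s.

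**By sex.** Assume 120 children per sex and half of sibling pairs of the same sex, so that the excess (Σm²/Σm − 1) is halved. The uncorrected half-width is 1.96 × 0.663 / √120 = ±0.119 s. Over the same mixes and ICC 0.1 to 0.5 it becomes ±0.120 to ±0.135 s, which is 1% to 14% wider.

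**By age band (reasoned, not calculated).** Many sibling pairs fall in different bands, and the two infant bands could hold little more than twins. Two siblings can, however, both be in the 5–12 band.

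**By skin tone (not quantified).** Siblings mostly stay in the same stratum, so cluster size is kept. Stratifying removes the part of the correlation that comes from shared tone. What remains is shared session and physiology, for which the documents offer no figure.

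**The case against.** The strongest objection is that nothing in the documents shows siblings enrolling in numbers. Open eligibility permits it, but the consent sentence, "We will obtain consent from one parent/legally authorized representative and assent from the participant if old enough", concerns how many adults sign, not how many children they bring. A reader might infer that the intervals are certain to be too narrow. The documents do not support that; the statement is conditional on siblings and on a positive correlation. Section 2.0 also reports marked age and sex variation in normal CRT, which would lower the raw correlation between siblings of different age or sex. This stands, and it makes the top of the range an extreme case.

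A reader might also infer from Section 16.9 that the analyst can never identify families. Sections 17.1 and 19.1 say otherwise: a name log, retained consents and accessible linkages exist. What is missing is a planned use of them.

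A third tempting reading is that the skin-tone intervals suffer most because siblings share tone. Within a stratum tone is nearly constant, so that source of correlation is largely gone.

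Two further points are fair. Room and operator effects are also shared by unrelated children seen in the same shift, and a family term would not address those. And no test or acceptance margin hangs on ±0.084 s, while the SD itself may be the larger uncertainty. If 0.663 s comes from the 19-adult pilot in Section 2.1 (not stated explicitly) and is treated as a simple SD on 18 degrees of freedom, its 95% interval is about 0.50 to 0.98 s, giving half-widths of ±0.063 to ±0.124 s. That puts the sibling effect in proportion. It does not remove it: a wrong planning SD is corrected once the observed SD is used, whereas ignored clustering remains in the reported intervals.

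**Conclusion.** The point holds in conditional form. The plan's intervals and half-widths assume unrelated children, the recruitment rules allow siblings, and the listed data have no family field. If siblings enrol and their CRTs are positively correlated, the mean CRT intervals will be too narrow.

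The size is small to moderate. Moderate assumptions, meaning mixes (a) and (b) with ICC up to 0.3, give an overall half-width of about ±0.085 to ±0.093 s, 2% to 11% wider than planned. The full assumed range, up to ICC 0.6, is about ±0.085 to ±0.106 s, at most 26% wider. The sex and age-band intervals are less affected, though age bands are not exempt, and the effect within skin-tone strata is unknown. All these figures rest on assumed family mixes and correlations. It is worth correcting because the remedy is cheap and leaves the intervals essentially unchanged if there are few siblings or no correlation.

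**What to change.** 1. Derive a de-identified family number from the eConsent records or the name-to-identifier log, and add it to the analysis data set and any shared data set. This version is dated 27 October 2022 and the stated recruitment window was 25 August to 5 September 2022, so for children already enrolled the number must be assigned retrospectively. Section 16.9 should be reconciled with Sections 17.1 and 19.1 so that this use of the log is plainly permitted.
2. In Section 15.3, specify family-clustered standard errors or a family random effect for the mean CRT intervals, overall and by age group, sex and skin tone.
3. Report the number of families alongside the number of children.
4. Label ±0.084 s and ±0.188 s as the half-widths for unrelated children.

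The cost is one added field, the work of assigning it, one analysis option, and intervals that may be slightly wider. No additional participants are needed.

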16.0 Health Information and Privacy Compliance

16.1 Select which of the following is applicable to your research:

MEDICAL PROTOCOL (HRP-590)

PROTOCOL TITLE: Capillary Refill Time Measurement Utilizing Mobile Application (Cap App) in Children
VERSION DATE: 10/27/2022

My research does not require access to individual health information and therefore assert HIPAA does not apply.

I am requesting that all research participants sign a HIPCO approved HIPAA Disclosure Authorization to participate in the research (either the standalone form or the combined consent and HIPAA Authorization).

I am requesting the IRB to approve a Waiver or an alteration of research participant authorization to participate in the research.

Appropriate Use for Research:

An external IRB (e.g. Advarra) is reviewing and we are requesting use of the authorization language embedded in the template consent form in lieu of the U of M stand-alone HIPAA Authorization. Note: External IRB must be serving as the privacy board for this option.

16.2 Identify the source of Private Health Information you will be using for your research (Check all that apply)

I will use the Informatics Consulting Services (ICS) available through CTSI (also referred to as the University's Information Exchange (IE) or data shelter) to pull records for me

I will collect information directly from research participants.

I will use University services to access and retrieve records from the Bone Marrow Transplant (BMPT) database, also known as the HSCT (Hematopoietic Stem Cell Transplant) database.

I will pull records directly from EPIC.

I will retrieve record directly from axiUm / MiPACS

I will receive data from the Center for Medicare/Medicaid Services

I will receive a limited data set from another institution

Other. Describe: Describe in detail the source of the information.

16.3 Explain how you will ensure that only records of patients who have agreed to have their information used for research will be reviewed.

Only participants who voluntarily approach our study team members with interest in participating in our study will be screened.

16.4 Approximate number of records required for review:

MEDICAL PROTOCOL (HRP-590)

PROTOCOL TITLE: Capillary Refill Time Measurement Utilizing Mobile Application (Cap App) in Children

VERSION DATE: 10/27/2022

We anticipate screening approximately 300 children for enrollment with a total enrollment goal of at least 240 participants, with aim for 48 in each of five age categories (1-3 months, 3-12 months, 1 - 5 years, 5-12 years, and 12-17). No access to the child's medical record will be required as enrolled during the D2D State Fair location.

16.5 Please describe how you will communicate with research participants during the course of this research. Check all applicable boxes

- This research involves record review only. There will be no communication with research participants.
- Communication with research participants will take place in the course of treatment, through MyChart, or other similar forms of communication used with patients receiving treatment.
- Communication with research participants will take place outside of treatment settings. If this box is selected, please describe the type of communication and how it will be received by participants. Participants will express interest in person by presenting to the D2D: The Driven to Discover Research Facility at the Minnesota State Fair.

16.6 Explain how the research team has legitimate access to patients/potential participants: The research team will be permitted to access sources of private information because all participants will be required to sign a HIPAA waiver at the time of informed consent.

16.7 Location(s) of storage, sharing and analysis of research data, including any links to research data (check all that apply).

- In the data shelter of the Information Exchange (IE)
 - Store Analyze Share
- In the Bone Marrow Transplant (BMT) database, also known as the HSCT (Hematopoietic Stem Cell Transplant) Database
 - Store Analyze Share
- In REDCap (recap.ahc.umn.edu)
 - Store Analyze Share
- In Qualtrics (qualtrics.umn.edu)
 - Store Analyze Share
- In OnCore (oncore.umn.edu)
 - Store Analyze Share

MEDICAL PROTOCOL (HRP-590)

PROTOCOL TITLE: Capillary Refill Time Measurement Utilizing Mobile Application (Cap App) in Children
VERSION DATE: 10/27/2022

In the University's Box Secure Storage (box.umn.edu)

Store

Analyze

Share

In an AHC-IS supported server. Provide folder path, location of server and IT

Store Analyze Share

In an AHC-IS supported desktop or laptop.

Provide UMN device numbers of all devices:

Store Analyze Share

Other: see mobile device below

Indicate if data will be collected, downloaded, accessed, shared or stored using a server, desktop, laptop, external drive or mobile device (including a tablet computer such as an iPad or a smartform (iPhone or Android devices) that you have not already identified in the preceding questions

I will use a server not previously listed to collect/download research data

I will use a desktop or laptop not previously listed

I will use an external hard drive or USB drive ("flash" or "thumb" drives) not previously listed

I will use a mobile device such as a smartphone not previously listed: The demographics, vital signs, underlying diagnosis, and CRT data (including video for the manual CRT measurement) will be collected from a smartphone which is running the Cap App mobile phone application. The data collected will be de-identified and uploaded to a secure Box platform hosted by UMN.

16.8 Consultants. Vendors. Third Parties. : A DUA will be signed to share de-identified research data with The University of Washington and The University of Toronto, who are collaborators on the CapApp.

16.9 Links to identifiable data:

All data will be de-identified. Study staff will assign an identification code for each participant to identify each individual record but it will not be used to link back to each individual participant. That same identification code will be transferred into the Box database. Any internal data reports will use only these codes and will not use any identifiable information. Any external data reports, abstracts, publications, presentations, etc. will present de-identified, grouped, and/or aggregate data. Any reports to the University of Minnesota IRB (such as Adverse Event reporting and annual renewal reports) will be kept confidential; they will not include participant- identifiable information; only the participant's identification code will be used

MEDICAL PROTOCOL (HRP-590)

PROTOCOL TITLE: Capillary Refill Time Measurement Utilizing Mobile Application (Cap App) in Children
VERSION DATE: 10/27/2022

- 16.10 Sharing of Data with Research Team Members Only* IRB-approved members of the study team will have access to the data through the methods already indicated in this section.
- 16.11 Storage of Documents:* Electronic documents will be stored in a secure database only accessible to research staff. We will maintain the de-identified patient characteristic data, de-identified video, and Cap App data for future use by other researchers (in UMN Box).
- 16.12 Disposal of Documents:* We will erase individual data forms from electronic smartphones upon transfer to Box file.

17.0 Confidentiality

17.1 Data Security:

Computers used will be University owned and meet University compliance requirements and pertinent external regulations. All computers are password protected and meet a basic level of security to protect the integrity of the data and network. These precautions also procure a high level of security to protect the integrity of the data and network as well as comply with OIT and data storage requirements within Fairview and the University of MN. Data will be stored on a password protected computer behind a firewall protected user drive.

Training: All study staff will be appropriately trained to this protocol and its requirements, including maintenance of participant confidentiality.

Authorization of access: Only designated IRB-approved staff will have access to the data. The data collected will not be reported to any medical provider nor provided to the patient or adult/legal guardian. The CRT measurements collected will be kept blinded to the participants and to the research staff and will not be interpreted or cause any change to the treatment or care of the child.

Password protection/encryption/physical controls: All data will be stored in the UMN Box system which is secured and HIPAA compliant. Consents will be retained in the HIPAA compliant REDCap platform that will only be accessed by the study team.

Confidentiality:

Individual participant information obtained because of this study is considered confidential. Information will be accessible to authorized parties or personnel only. All records will be identified in a manner designed to maintain participant confidentiality.

No paper records will be kept.

Separation of Identifiers and data:

MEDICAL PROTOCOL (HRP-590)

PROTOCOL TITLE: Capillary Refill Time Measurement Utilizing Mobile Application (Cap App) in Children
VERSION DATE: 10/27/2022

Participants will be assigned a unique identifier. Any participant records or datasets will contain the identifier only; participant names and associated unique identifier will be kept on a separate log (Box). The capillary refill measurements will be kept blinded to the research team member and no action will be taken on aberrant measurements.

